10.2.1.6 Adverse Events of Special Interest

The Adverse Events of Special Interest (AESI) categories will be summarized and presented by "as treated" treatment group and overall using SOC and MedDRA PT. The AESI categories will be identified by the following search criteria per Standard MedDRA Queries (SMQs)/Company MedDRA Queries (CMQs) in [Table 10](#) below.

Table 10. AESI for Upadacitinib with SMQs/CMQs/PTs Searches

AESI	Type of MedDRA Query	Broad or Narrow Search	SMQ/CMQ Search Criteria
Serious Infections	CMQ		"Infections" – Subset for SAEs
Opportunistic Infection	CMQ		"Opportunistic Infection"
Possible Malignancy	SMQ	Narrow	"Malignancies"
Malignancy	SMQ		"Malignant tumours"
Non-Melanoma Skin Cancer (NMSC)	SMQ	Broad	Skin Malignant tumours (Broad SMQ) removing Melanoma CMQ
Malignancy excluding NMSC			"Malignant tumours" SMQ removing NMSC output
Lymphoma	SMQ		"Malignant Lymphomas"
Hepatic Disorder	SMQ	Narrow	"Drug Related Hepatic Disorders"
Gastrointestinal Perforations	SMQ	Narrow	"Gastrointestinal Perforation"
Anemia	CMQ		"Non-Hemolytic and Non-Aplastic Anemias"
Neutropenia	CMQ		"Hematological Toxicity – Neutropenia"
Lymphopenia	CMQ		"Hematological Toxicity – Lymphopenia (Veliparib Product Specific)"
Herpes Zoster	CMQ		"Herpes Zoster"
Creatine Phosphokinase (CPK) Elevation	PT		Search only for the PT of "Blood creatine phosphokinase increased"
Renal Dysfunction	SMQ	Narrow	"Acute Renal, Failure"
Tuberculosis	CMQ		"Tuberculosis"
Adjudicated Cardiovascular Events	Output from CAC		
MACE*			
Undetermined/Unknown Cause of Deaths			

Table 10. AESI for Upadacitinib with SMQs/CMQs/PTs Searches (Continued)

AESI	Type of MedDRA Query	Broad or Narrow Search	SMQ/CMQ Search Criteria
Other Cardiovascular events			
Venous Thromboembolic Events**			
Other Venous Thrombosis			
Arterial Thromboembolic Events (non-cardiac, non-neurologic)			

* MACE; Major Adverse Cardiovascular Events, defined as cardiovascular death, non-fatal myocardial infarction and non-fatal stroke.

** Venous thromboembolic events (VTE) include deep vein thrombosis (DVT) and pulmonary embolism (PE).

Additional AEs may be considered for tabulation/summary based on recommendations from Clinical and Safety as deemed appropriate.

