### **6.1 Medical Complaints**

The Investigator will monitor each subject for clinical and laboratory evidence of AEs on a routine basis throughout the study. The Investigator will assess and record any AE in detail including the date of onset, event diagnosis (if known) or sign/symptom, severity, time course (end date, ongoing, intermittent), relationship of the AE to study drug, and any action(s) taken. For SAEs considered as having "no reasonable possibility" of being associated with study drug, the Investigator will provide other cause(s) of the event. For

AEs to be considered intermittent, the events must be of similar nature and severity. AEs, whether in response to a query, observed by site personnel, or reported spontaneously by the subject will be recorded.

All AEs will be followed to a satisfactory conclusion.

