### **6.1.1.3 Adverse Events of Special Interest**

The following AEs of special interest will be monitored during the study (see detailed toxicity management in Section 6.1.7):

- Serious infections
- Opportunistic infections
- Herpes Zoster
- Tuberculosis
- Malignancy (all types)
- Gastrointestinal Perforations
- Adjudicated cardiovascular events (e.g., major adverse cardiovascular event [MACE])
- Lipid Profile Changes
- Anemia
- Neutropenia
- Lymphopenia
- Increased serum creatinine and renal dysfunction
- Hepatic events and increased hepatic transaminases
- Elevated creatine phosphokinase (CPK)
- Embolic and thrombotic events (non-cardiac, non-CNS)

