Serum Creatinine	
 
• If serum creatinine is <math>> 1.5 \times</math> the baseline value and <math>> \text{ULN}</math>, repeat the test for serum creatinine (with subject in an euvoletic state) to confirm the results. If the results of the repeat testing still meet this criterion then interrupt study drug and re-start study drug once serum creatinine returns to <math>\leq 1.5 \times</math> baseline value and <math>\leq \text{ULN}</math>.
 
• If confirmed serum creatinine <math>\geq 2</math> mg/dL, interrupt study drug and re-start study drug once serum creatinine returns to normal reference range or its baseline value.
 
 
For the above serum creatinine elevation scenarios, complete supplemental renal eCRF.

Creatine Phosphokinase	
 
• If confirmed CPK <math>\geq 4 \times</math> ULN and there are no symptoms suggestive of myositis or rhabdomyolysis, the subjects may continue study drug at the investigator's discretion.
 
• If CPK <math>\geq 4 \times</math> ULN accompanied by symptoms suggestive of myositis or rhabdomyolysis, interrupt study drug and contact AbbVie TA MD
 
 
For the above CPK elevation scenarios, complete supplemental CPK eCRF.

For allowed study drug interruption, the following rules apply:

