#### **8.1.5.2.1 Treatment-Emergent Adverse Events (TEAE)**

AEs will be coded using MedDRA. A TEAE is defined as AE that began or worsened in severity after initiation of study drug.

AEs starting more than 70 days following the last dose of study drug for subjects on ADA and AEs starting more than 30 days following the last dose of study drug for subjects on upadacitinib or placebo will not be included in summaries of TEAEs. For subjects who continued into Period 2, the AEs that are reported in Period 2 will be summarized in the long term safety analysis.

As a general safety summary, the number and percentage of subjects experiencing TEAEs will be summarized for each treatment group for the following AE categories:

- All AEs;
- All severe AEs;
- All reasonably possibly related AEs;
- All SAEs;
- Frequent AEs (reported in 2% of subjects or more in any treatment group);
- Frequent reasonably possibly related AEs (reported in 2% of subjects or more in any treatment group);
- Discontinuations due to AEs;
- Death.

Additional AEs may be considered for tabulation/summary based on recommendations from Clinical and Safety as deemed appropriate.

TEAEs will be summarized and presented by system organ classes (SOCs) and preferred terms (PTs) using MedDRA. The SOC's will be presented in alphabetical order, and the PTs will be presented in alphabetical order within each SOC.

TEAE will also be summarized by maximum severity and by maximum relationship.

The AEs of special interest (including but not limited to serious infection, opportunistic infection, herpes zoster, TB, gastrointestinal perforations, malignancies, MACE, renal dysfunction, anemia, increased CPK, non-cardiac, non-CNS embolic and thrombotic events, and drug-related hepatic disorders) will be summarized. Event rate (per 100 patient years) for AEs of special interest will also be summarized for the combined safety analysis of Period 1 and Period 2.

All AEs leading to discontinuation of study drug will be presented in listing format. A listing by treatment group of TEAEs grouped by SOC and MedDRA preferred term with subject identification numbers will be generated.

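### SAP Table 10 has no search for the increased-creatinine element of the protocol's renal AESI, so those adverse events are not shown to reach the AESI analyses

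*SAP*

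**What the plan says.** Protocol 6.1.1.3 introduces its list with "The following AEs of special interest will be monitored during the study (see detailed toxicity management in Section 6.1.7"). Two of its entries matter here: "Increased serum creatinine and renal dysfunction" and "Elevated creatine phosphokinase (CPK"). In Section 6.1.7, Table 7 sets interruption rules for creatinine rises on their own and asks for the supplemental renal form when they occur. It treats a CPK value at or above 4 × ULN differently when it is "accompanied by symptoms suggestive of myositis or rhabdomyolysis, interrupt study drug and contact AbbVie TA MD".

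The protocol's analysis section, 8.1.5.2.1, gives a shorter list of AESIs to be summarized, ending "renal dysfunction, anemia, increased CPK, non-cardiac, non-CNS embolic and thrombotic events, and drug-related hepatic disorders". That list is expressly open-ended.

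SAP 10.2.1.6, Table 10, turns the AESIs into searches. The row called Renal Dysfunction uses a Narrow standard MedDRA query, "Acute Renal, Failure". The CPK row is a single preferred term: "Search only for the PT of 'Blood creatine phosphokinase increased". There is no row for creatinine.

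An AESI receives outputs that other events do not: treatment differences in percentages with 95% CI (SAP 10.2.1.1), grouped tables (10.2.1.6), treatment differences in rates per 100 patient-years with 95% CI (10.2.2.1), and AESI rates (10.2.2.3).

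**The concern.** The protocol's renal AESI has two elements, and increased serum creatinine is the one named first. The SAP search addresses the other element, and only in the form of acute failure as far as the query's label shows. If the query does not hold the increased-creatinine term, an investigator-reported creatinine rise counts as nothing on the renal AESI line. The between-group comparison planned for that line then describes a smaller concept than the one the protocol said would be monitored. A reader of the study report would have no way to see this from the table label.

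A second, lesser matter sits in the CPK row. Protocol 6.1 has sites record "event diagnosis (if known) or sign/symptom", so a muscle event can enter the database as a diagnosis with no separate CPK term.

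**Working it through.** No arithmetic applies: the plan gives no event rate or query content to compute from. The check sets the two documents side by side for the AESIs that have a laboratory basis.

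| Protocol 6.1.1.3 | Named in protocol 8.1.5.2.1? | SAP Table 10 row | Search |
|---|---|---|---|
| Increased serum creatinine | No | None | None |
| Renal dysfunction | Yes | Renal Dysfunction | Narrow standard query on acute renal failure |
| Elevated CPK | Yes | CPK Elevation | One preferred term |
| Anemia | Yes | Anemia | Company query |
| Neutropenia | No | Neutropenia | Company query |
| Lymphopenia | No | Lymphopenia | Company query |
| Hepatic events and raised transaminases | Yes, as drug-related hepatic disorders | Hepatic Disorder | Narrow standard query |
| Lipid profile changes | No | None | None |

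1. **Renal row.** The creatinine element has no counterpart in Table 10. Its absence from 8.1.5.2.1 does not explain this: neutropenia and lymphopenia are also absent there, yet each has a Table 10 row. The SAP therefore did not treat that shorter list as the limit.

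2. **Drafting order.** The protocol synopsis is dated 01 December 2017 and the SAP 07 December 2017. Protocol Section 1.1 says Amendment 5 revised the AESI list to match a product-level safety SAP, and the creatinine wording was kept. The mismatch is not explained by an outdated protocol list.

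3. **Tracing one event.** Suppose a site reports an increased creatinine as an adverse event.
   - It appears in the all-event tables by system organ class and preferred term, and in the serious, severe, related and discontinuation versions where these apply (SAP 10.2.1.2).
   - It has a rate per 100 patient-years by preferred term (10.2.2.2). If serious or leading to discontinuation, it is listed (10.2.2.4).
   - The laboratory value itself is graded, enters the shift tables and, at Grade 3 or 4, is counted and listed (10.3.2.2, 10.3.2.3, 10.3.3.2).
   - It enters the AESI outputs of 10.2.1.1, 10.2.1.6, 10.2.2.1 and 10.2.2.3 only if the acute renal failure query contains its term. The documents do not show that it does.

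   The routes outside the AESI set give counts, percentages or rates. None of them plans a treatment difference with a confidence interval.

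4. **CPK row.** The protocol AESI, its short form in 8.1.5.2.1, and the trigger for the supplemental form in Section 6.1.4 are all defined by the CPK increase. The single preferred term matches that definition. Because the row is restricted to that one term, an event entered only as rhabdomyolysis or myositis falls outside it. The protocol does not list those diagnoses as AESIs.

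**The case against.** Five points can be made for leaving Table 10 alone.

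- **The query content is not in the documents.** This stands. A reader might infer that creatinine events are certainly missed; the label suggests it but cannot prove it. The supportable statement is that capture is not shown.
- **The SAP places some laboratory-type AESIs in its laboratory sections.** Lipid changes have no Table 10 row but receive change and percent-change summaries. Transaminases receive threshold counts in 10.3.2.4. Recording a creatinine rise as an adverse event is largely at the investigator's discretion (protocol 5.3.1.1, Clinical Laboratory Tests), so graded values may be the more complete measure. This is a fair account of what may have been intended, but the SAP does not say it. Anemia, neutropenia, lymphopenia and CPK all have both laboratory analyses and an event search.
- **The events are visible elsewhere.** This stands, and it limits the consequence. Seriousness, relatedness and rates by preferred term are all tabulated.
- **Additional events may be tabulated on advice from Clinical and Safety.** That clause is optional and prespecifies nothing.
- **Muscle injury is not a protocol AESI.** This stands. A reader might infer from the single-term restriction that the CPK search is narrower than the protocol's AESI. It is not: both are defined by the enzyme elevation. Nor does anything stop a site from recording the CPK rise alongside the diagnosis.

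**Conclusion.** The point holds for the renal AESI. One of its two protocol-named elements has no stated search, so adverse events of increased creatinine are not shown to be included in the AESI groupings, differences or rates. The consequence is moderate: a planned between-group estimate is missing for that element, but the events do not disappear from the safety report. No subject count can be attached, because any figure would need both a creatinine event rate and the query's term list, and neither is given. The conclusion assumes only that the Narrow query is not already known to contain the increased-creatinine term. If the term list shows that it does, what remains is a labelling and transparency matter.

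For CPK there is no mismatch between protocol and SAP, only an optional improvement.

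**What to change.** Leave the renal row as it is. Add a separate, prespecified line to Table 10 for the preferred term for increased blood creatinine, with the same outputs as other AESIs: treatment difference in percentages with 95% CI, treatment difference in rates with 95% CI, and rates per 100 patient-years. Attach the term list behind the renal query with its MedDRA version, so that any overlap between the two lines is visible. If the sponsor means this element to be assessed from laboratory data alone, the SAP should at least say so and give the reason. Either change belongs before the Week 26 unblinding.

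Optionally, add a supportive muscle-injury line (preferred terms for rhabdomyolysis, myositis and myopathy) beside the CPK row, labelled as supplementary to the protocol's AESI.

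The cost is a few search terms and table rows, with no new data collection. The creatinine term is less specific than acute renal failure and will raise the AESI count slightly; a separate line keeps that visible. Leaving the existing rows unchanged also preserves whatever comparability they have with the product-level safety plan, which is not among the documents.

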10.2.2 Analysis of Long-Term Adverse Event Rates

Long-term adverse event rates will be analyzed using event rates adjusted by cumulative exposure and will be based on the actual treatment received at the time of AE occurrence. Two sets of summaries, "summary based on all study drug exposure" and "summary based on long-term study drug," respectively, will be provided following the treatment groups as described in Section 10.1.3.

10.2.2.1 Overview of Adverse Events Rates per 100 Patient-Years of Study Drug Exposure

An overview of AEs per 100 patient-years of study exposure will be presented by treatment group and overall for the following AE categories.

- All TEAEs
- Treatment-emergent serious adverse events (SAEs)
- Treatment-emergent severe adverse events
- TEAEs reasonably possibly related to study drug

- TEAEs of special interest
- TEAEs leading to discontinuation of study drug
- TEAE leading to death

For this calculation, one year will be considered to be 365.25 days. For each treatment group, the numerator of the overall rate will be the total number of TEAEs reported for the event; that is, a subject can contribute more than one event to the numerator. For each treatment group, the denominator of the rates will be the total number of days exposed to study drug summed across all treated subjects divided by 365.25. Please refer to Section 6.0 for the calculation of study drug exposure. The AE rate per 100 patient-years of exposure will be calculated as $(\text{[numerator/denominator]}) \times 100$. The number of AEs reported (numerator), the total number of years of study drug exposure (denominator), and the AE rate per 100 patient-years will be presented for each treatment group and overall.

Additional AEs may be considered for tabulation/summary based on recommendations from Clinical and Safety as deemed appropriate.

For TEAEs of special interest, the point estimate and 95% CI (using normal approximation) will be provided for the treatment difference in AE rates per 100 patient-years.

10.2.2.2 Adverse Events Rates per 100 Patient-Years of Study Drug Exposure by SOC and PT

For each treatment group, the TEAE rate per 100 patient-years of exposure will be calculated overall, for each SOC and each PT, for each of the following events:

- All TEAEs
- Treatment-emergent serious adverse events (SAEs)
- Treatment-emergent severe adverse events
- TEAEs reasonably possibly related to study drug
- TEAEs leading to discontinuation of study drug
- TEAE leading to death

For this calculation, 1 year will be considered to be 365.25 days. For each treatment group, the numerator of the overall rate, the SOC rate, or the PT rate, will be the total number of TEAEs reported overall, for the SOC, or for the PT, respectively; that is a subject can be counted more than once overall, for a SOC, and for a PT. For each treatment group, the denominator of the rates will be the total number of days exposed to study drug summed across all treated subjects divided by 365.25. Please refer to Section 6.0 for the calculation of study drug exposure. The AE rate per 100 patient-years of exposure will be calculated as $[(\text{numerator}/\text{denominator})]*100$. The number of AEs reported (numerator), the total number of years of study drug exposure (denominator), and the AE rate per 100 patient-years will be presented overall, for each SOC, and for each PT for each treatment group.

10.2.2.3 Adverse Events of Special Interest Rates per 100 Patient-Years of Study Drug Exposure

The Adverse Events of Special Interest (AESI) categories will be summarized and presented for each treatment group and overall using SOC and MedDRA PT. The AESI categories will be identified per Standard MedDRA Queries (SMQs)/Company MedDRA Queries(CMQs).

For each treatment group, the Adverse Events of Special Interest (AESI) rate per 100 patient-years of exposure will be calculated overall, for each SOC and each PT, for each of the AESI listed in Section [10.2.1.6](#).

For this calculation, one year will be considered to be 365.25 days. For each treatment group, the numerator of the overall rate, the SOC rate, or the PT rate, will be the total number of TEAEs reported overall, for the SOC, or for the PT, respectively; that is a subject can be counted more than once overall, for a SOC, and for a PT. For each treatment group, the denominator of the rates will be the total number of days exposed to study drug summed across all treated subjects divided by 365.25. Please refer to Section [6.0](#) for the calculation of study drug exposure. The AE rate per 100 patient-years of exposure will be calculated as $[(\text{numerator}/\text{denominator})]*100$. The number of AEs

reported (numerator), the total number of years of study drug exposure (denominator), and the AE rate per 100 patient-years will be presented overall, for each SOC, and for each PT for each treatment group.

10.2.2.4 Listing of Serious Adverse Events (Including Deaths) and Adverse Events Leading to Study Drug Discontinuation

All serious adverse events (SAEs), deaths, and adverse events leading to discontinuation of study drug will be listed.

10.3 Analysis of Laboratory Data

10.3.1 Variables and Units

All laboratory parameters to be collected in this study are listed below. Laboratory parameters will be reported using the standard international (SI) units.

Table 11. List of Laboratory Variables

Laboratory Variables

Hematology

White Blood Cell (WBC) Count

Red Blood Cell (RBC) Count

Hemoglobin

Hematocrit

Platelets count

Neutrophils

Basophils

Eosinophils

Lymphocytes

Monocytes

Bands

Chemistry

Total Bilirubin

Alkaline Phosphatase (ALP)

Serum glutamic oxaloacetic transaminase/aspartate aminotransferase (SGOT/AST)

Serum glutamic pyruvic transaminase/alanine aminotransferase (SGPT/ALT)

Total Protein

Albumin

Glucose

Triglycerides

Blood Urea Nitrogen (BUN)

Creatinine

Uric acid

Sodium

Potassium

Calcium

Inorganic Phosphorus

Creatine Phosphokinase (CPK)

Chloride

Bicarbonate

Table 11. List of Laboratory Variables (Continued)

Laboratory Variables
Chemistry (continued)
Cholesterol (TC)
LDL cholesterol (LDL-C)
HDL cholesterol (HDL-C)
LDL-C/HDL-C ratio
TC/HDL-C ratio
Urinalysis
Specific Gravity
pH
Protein
Glucose
Ketones
Blood
Microscopic Examination (if needed)
Urobilinogen
Bilirubin
Leukocytes
Nitrites
Other
hs-CRP
QuantiFERON-TB Gold ^a
IgG and IgM
ESR

a. For annual follow-up QFT is captured only for those with negative QFT at Screening.

10.3.2 Analysis of Short-Term Laboratory Data

Two sets of analysis will be conducted for short-term laboratory data (unless otherwise specified), namely "safety analysis up to Week 14" and "safety analysis up to Week 26 censored at treatment switching" as outlined in Section 10.1.1 and Section 10.1.2. Data

will be summarized by "as treated" treatment group (placebo, ADA 40 mg EOW, Upadacitinib 15 mg QD).

10.3.2.1 Assessment of Mean Change from Baseline in Clinical Laboratory Variables

Analyses of mean change from baseline in continuous hematology, chemistry, and urinalysis variables which are measured longitudinally will be performed by visits and by "as treated" treatment group. For each change from baseline analysis, the following summary statistics will be presented for each treatment group: sample size, baseline mean, visit mean, and the mean, standard deviation, and median of the changes from baseline.

In addition, similar analyses will be conducted for percentage change from baseline in hemoglobin, LDL-C, HDL-C and triglycerides.

Analysis of mean change and mean percent change by visit will only be provided for "safety analysis up to Week 26 censored at treatment switching." Analysis will not be repeated for "safety analysis up to Week 14," because it will be a subset of the former.

10.3.2.2 Assessment of Shift from Baseline in Clinical Laboratory Variables

The baseline and post-baseline laboratory observations will be categorized as Grade 1, Grade 2, Grade 3, and Grade 4 according to OMERACT criteria (Rheumatology Common Toxicity Criteria v.2.0). For creatine phosphokinase and creatinine, NCI CTC criteria will be used.

For each laboratory variable, shift tables will be generated that cross tabulate the subjects' as deemed appropriate by "as treated" treatment group:

- Category of the baseline value versus category of the final value.
- Category of the baseline value versus maximum category.
- Category of the baseline value versus minimum category.

Note that the minimum/maximum category is used, rather than the category of the minimum/maximum value. The two may be different due to variation in the reference range.

No statistical tests will be performed for this analysis.

